### 4. STATISTICAL METHODS

#### 4.1 Demographics and Baseline Characteristics

Summary statistics, including mean, standard deviation, median, minimum, and maximum on continuous demographic and baseline characteristic variables will be obtained for the ITT and PP populations. Categorical demographic and baseline variables will be summarized with frequencies and percentages for the ITT and PP populations.

Continuous variables will be evaluated for normality using Q-Q plots. Two sample t-test will be used to examine differences between the two study arms (B. breve vs. placebo) if the normality assumption is satisfied, and Wilcoxon rank sum test will be used otherwise. Categorical variable distribution between study arms will be assessed by Chi-squared or Fisher's exact test, as appropriate.

The demographic and baseline variables may include but not limited to:

- Age (years)
- Gender (male, female)
- Race
- Ethnicity

#### **4.2 Compliance**

The IP compliance will be assessed by counting the returned unused test product at each visit. The IP compliance is calculated by determining the number of dosage units taken divided by the number of dosage units expected to have been taken multiplied by 100.

$$\frac{\text{number of dosage units taken}}{\text{number of dosage units expected to have been taken}} \times 100\%$$

Possible differences in the IP compliance between B. breve and placebo groups will be assessed by two-sample t-test if the normality assumption is satisfied, and Wilcoxon rank sum test will be used otherwise.

Compliance will also be assessed for exercise.

#### **4.3 Protocol Deviations**

Protocol deviations will be listed in the final study report.

#### **4.4 Level of significance**

The significance level for this study will be  $p \leq 0.05$  (5%).

## 5. EFFECTIVENESS/ EFFICACY ANALYSIS

### 5.1 Primary outcomes

Primary Outcomes	Hypothesis
1- The difference in change in fat loss from baseline (% or g), as assessed by DXA, between B. breve and placebo after 12 weeks of supplementation.	H0: There is no difference in mean change in fat loss, as assessed by DXA, from baseline at week 12 between B. breve and placebo

Summary statistics including number of participants, mean, median, standard deviation, minimum, and maximum will be obtained for baseline and week 12 visits. Similar summary statistics will be obtained for the change from baseline to week 12. Mean values will be displayed as graphs, with a separate line for each product, and error bars indicating  $\pm$  SEM. Mean changes from baseline will also be graphed similarly.

The primary outcome will be assessed using ANCOVA, with the baseline measurements as covariate and group as the factor variable. The dependent variable will be the change from baseline at week 12. Q-Q plots and residuals versus fitted values plots will be generated for the evaluation of the model adequacy. If the residual plots show violation of the model assumptions, log or other transformation of the dependent variable will be performed.

Between group differences will be assessed by two-sample t- test. If the outcome is not normally distributed, then Wilcoxon rank sum test will be used.

Within group differences will be assessed by paired t-test if the outcome is normally distributed and Wilcoxon signed rank test otherwise. P-values and 95% confidence intervals will be calculated.

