**8.6 Randomization**

A randomization schedule will be created and provided to the Investigator indicating the order of randomization. Each participant will be assigned a randomization code according to the order of the randomization list generated using [www.randomization.com](http://www.randomization.com). Enrolled participants will be randomized to the different study arms at Day 0.

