## 12 STATISTICAL EVALUATION

### 12.1 Determination of Sample Size

With a total sample size of 100 (50 per group; 40 completers), it is possible to detect a difference in mean change in percent body fat or body fat mass of 0.76% or 0.79 kg respectively, in a parallel design at a two-sided unadjusted 5% significance level, 80% power and 20% attrition rate. This calculation is based on standard deviations of 1.19% and 1.24 kg for percent body fat and body fat mass respectively, estimated from a study by Minami et al (2018).

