### 12.3 Statistical Analysis Plan

For each continuous endpoint including percent body fat, body fat mass, visceral fat area, weight, BMI, total cholesterol, HDL-cholesterol, LDL-cholesterol, triglycerides, waist circumference, and hip circumference, fasting blood glucose, HbA1c, fasting insulin levels, AST, ALT, GGT, ALP, a summary table will be prepared with a variety of summary statistics including mean, standard deviation, median, min-max range and number of participants analyzed for each time point-treatment pairing. These data will be classified in subgroups based on the similarity of microbiota composition.

To account for any a priori differences between groups, the similar summary statistics of the changes from baseline will also be provided. Mean values will be displayed as graphs, with a separate line for each product, and error bars indicating  $\pm$  SEM. Mean changes from baseline will also be graphed similarly. Changes in continuous endpoints from screening/baseline will be calculated as:

$$\text{Change to } V_i = \text{Value at } V_i - \text{Value at } V_{\text{screening/baseline}}$$

Continuous variables will be tested for normality and log-normality using histograms, box plots and Q-Q plots. Log-normally distributed variables will be analyzed in the logarithmic domain. Summary statistics will be provided as non-transformed values. Intractably non-normal variables will be analyzed by appropriate non-parametric tests.

Protocol 20BWHM:

A randomized, double-blind, placebo-controlled study to investigate the effects of a *Bifidobacterium breve* strain on fat loss in healthy adults

The primary endpoint - change in fat loss from baseline (%) or g), as assessed by Dual-Energy X-Ray Absorptiometry (DXA), between *B. breve* and placebo after 12 weeks of supplementation - will be assessed for between-group differences using ANCOVA, with the baseline measurements as covariate.

Continuous secondary endpoints will be tested for between-group differences using repeated measures linear mixed-effects ANCOVA. This will allow for the random effects associated with each subject to be accounted for. The dependent variable will be the change at each visit, the fixed effects will be the study group \* visit number, and the covariate will be the dependant variable at baseline (Day 0).

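### Sex is collected but is in neither the primary ANCOVA nor the described randomisation; prespecifying it as a covariate is a minor, nearly free gain in precision

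*SAP*

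**What the plan says.** SAP 5.1 models the change in fat at week 12 by ANCOVA, "with the baseline measurements as covariate and group as the factor variable". Protocol 12.3 gives the same model, "using ANCOVA, with the baseline measurements as covariate". Neither names sex, and sex is in none of the secondary efficacy models.

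SAP 4.1 includes "Gender (male, female" among the baseline variables and compares categorical baseline variables between arms by chi-squared or Fisher's exact test. Nothing in the analysis depends on the result.

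Protocol 8.6 describes one list: "Each participant will be assigned a randomization code according to the order of the randomization list". It mentions no stratification by sex.

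Inclusion criterion 5 (protocol 1.1 and 7.1) sets sex-specific fat limits. On DXA they are 30% for women and 20% for men; on BIA at screening, 25% and 15%.

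**The concern.** The eligibility rules treat the same fat percentage as meaning different things in men and women, yet the model puts both sexes on one line of change against baseline fat. Two costs could follow.

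- **Precision.** If sex predicts change among people with equal baseline fat, that variation stays in the residual. This can happen even when men and women have the same mean change: if fatness relative to one's own sex is what predicts change, a pooled slope is too shallow within each sex.
- **Conditional balance.** With sex left to chance in both the allocation and the model, an uneven split shifts the estimate in the trial actually run, to the extent that baseline fat does not absorb it.

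Prespecification matters too. If the SAP 4.1 table shows an imbalance, adjusting for sex at that stage would be a post hoc choice.

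**Working it through.** **Inputs from the documents (protocol 12.1).** "total sample size of 100 (50 per group; 40 completers"; "two-sided unadjusted 5% significance level, 80% power and 20% attrition rate"; the design can "detect a difference in mean change in percent body fat or body fat mass of 0.76% or 0.79 kg respectively", with "standard deviations of 1.19% and 1.24 kg for percent body fat and body fat mass respectively".

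**Assumptions, not in the documents.** Half the participants are women. Mean baseline fat differs by 10 points between the sexes (borrowed from the entry limits, which are floors and not means). Within-sex SD w of baseline fat is 3 to 6 points. Women and men differ in change by g points at equal baseline fat, with g = 0.5 as the main case. The planning SD of 1.19 is taken as the residual SD of the model without sex.

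**1. The plan's own figure.** SE = 1.19 × √(2/40) = 0.266. Power by noncentral t is 80.5% for 0.76 points and 80.3% for 0.79 kg. The differences detectable with exactly 80% power are 0.755 points and 0.787 kg, which round to those stated, and 40/(1 − 0.20) = 50. The sample size reproduces without sex in the model.

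**2. Cost of the term.** If sex has no effect, residual degrees of freedom fall from 77 to 76 and power from 80.52% to 80.51%.

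**3. How much of sex baseline fat already carries.** Share = 0.25 × 10² / (0.25 × 10² + w²) = 25/(25 + w²).
- w = 3: 25/34 = 0.735
- w = 6: 25/61 = 0.410

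So 26.5% to 59% of the variance of sex is left over on the percentage scale. On the gram scale the documents give no sex difference in baseline fat, so the overlap cannot be sized.

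**4. Gain in precision.** Variance that sex would remove: v = g² × 0.25 × (1 − share). Partial R² = v/1.19² = v/1.4161. New SD = 1.19 × √(1 − R²).

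| Case | Partial R² | Power at 0.76 |
|---|---|---|
| No sex effect at equal baseline | 0 | 80.5% |
| g = 0.5, w = 3 | 0.0625 × 0.265/1.4161 = 0.012 | 81.0% |
| g = 0.5, w = 6 | 0.0625 × 0.590/1.4161 = 0.026 | 81.5% |
| R² set at 0.05 | 0.05 | 82.5% |
| R² set at 0.10 | 0.10 | 84.4% |

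The last row needs a large effect. Even with w = 6, g = √(0.10 × 1.4161/(0.25 × 0.590)) = 0.98 points, which exceeds the 0.76 that the trial is sized to detect.

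**5. The pooled slope.** Suppose mean change is equal in both sexes, w = 5, and baseline fat correlates 0.3 with change within each sex. The within-sex R² is 0.3² = 0.09. The pooled slope captures a share 25/(25 + 25) = 0.5 of that, or 0.045. Partial R² of sex is (0.09 − 0.045)/(1 − 0.045) = 0.047, and power is about 82.3%. This is the same g in another form: equal mean change across a 10-point gap implies a difference at equal baseline of (0.3 × 1.19/5) × 10 = 0.71 points.

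**6. Chance imbalance.** Take the number of women per arm as binomial (40, 0.5). The split then differs by at least 10 points with probability 43%, and by at least 20 points with probability 9%. For a 20-point imbalance and g = 0.5, the shift left after baseline adjustment is 0.20 × 0.5 × (1 − share):
- w = 3: 0.10 × 0.265 = 0.03 points
- w = 6: 0.10 × 0.590 = 0.06 points

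That is 3% to 8% of 0.76, or 0.10 to 0.22 of the SE.

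**7. Validity.** In simulations of 4,000 trials (within-sex residual SD 1.19, w = 5), type I error was 5.4% in both models with no sex effect and 5.1% in both with g = 0.6. Power without and with sex was 79.5% and 79.3% (g = 0), 80.8% and 80.7% (0.3), 79.2% and 80.3% (0.6), and 76.6% and 79.1% (1.0). The mean estimate stayed near 0.76 in both models.

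**The case against.** The strongest reply is that the planned model is valid and standard. The 10-point gap is between entry limits for the level of fat, the outcome is change, and baseline fat is already a covariate. No figure in either document says that sex predicts change at equal baseline, so the gain could be nil. All of this stands, and it is why the point is minor.

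It also rules out three stronger readings that a reader might infer:

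- **That the differing limits prove precision is being lost.** They do not; only a sex difference in change at equal baseline would, and the documents report none.
- **That a sex imbalance goes wholly uncorrected.** On the percentage scale the baseline covariate absorbs part of it. If 0.5 points is taken as the raw sex difference in mean change, a 20-point imbalance gives 0.20 × 0.5 = 0.10 points, 13% of 0.76, but only in an unadjusted contrast. That would apply to the two-sample t-test also listed in SAP 5.1, not to the ANCOVA.
- **That a sex term can only help.** With no sex effect it gains nothing and costs a degree of freedom, though the loss is negligible.

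The reply does not dispose of the pooled slope. Baseline fat makes sex redundant only if the sex difference in mean change equals the within-sex slope times the baseline gap, and nothing in the documents suggests that it does.

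**Conclusion.** A minor, nearly free improvement. The omission is plain in both documents: sex is collected and tested between arms, but neither modelled nor described as a stratification factor. At the planned difference of 0.76 the likely benefit is small: nil if sex is irrelevant at equal baseline, about 0.5-1 power point for a 0.5-point difference, and about 4 points if sex explains 10% of residual variance. A 20-point imbalance, with about a 9% chance, would move the adjusted estimate by about 0.03-0.06 points in the 0.5-point case.

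These sizes rest on the assumed sex mix, baseline gap, within-sex SD and sex effect, none of which the documents give. Chance imbalance under randomisation neither biases the comparison nor inflates type I error, and the stated sample size holds without the change.

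**What to change.** In SAP 5.1 and protocol 12.3, specify the primary model as: *ANCOVA of week-12 change with baseline value and sex as covariates and group as factor.* Make the change before unblinding so that adjustment for sex is prespecified whatever the baseline table shows.

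The cost is one model term and one degree of freedom, with no new data and no change to the sample size. Stratifying the randomisation by sex is optional if the list has not been generated, and the fix does not depend on it.

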### 5.2 Secondary Outcomes

Secondary Outcomes	Hypothesis
1. The difference in change from baseline between B. breve and placebo in body composition (weight, BMI, android/gynoid fat ratio, and muscle mass (% or g)) as assessed by DXA after 12 weeks of supplementation	H01.1: There is no difference in mean change in body composition (weight, BMI, android/gynoid fat ratio, and muscle mass (% or g)) as assessed by DXA from baseline at week 12 between B. breve and placebo
2. The difference in change from baseline between B. breve and placebo in waist circumference, hip circumference, and	H02.1: There is no difference in mean change in waist circumference, hip circumference, and waist/hip

waist/hip circumference ratio after 6 and 12 weeks of supplementation	
circumference ratio from baseline at week 6 between B. breve and placebo
 
H02.2
 
There is no difference in mean change in waist circumference, hip circumference, and waist/hip circumference ratio from baseline at week 12 between B. breve and placebo

3. The difference in change from baseline between B. breve and placebo in Lipid profile (total cholesterol, HDL-cholesterol, LDL-cholesterol, triglycerides) after 12 weeks of supplementation	
H03.1:
 
There is no difference in mean change in Lipid profile (total cholesterol, HDL-cholesterol, LDL-cholesterol, triglycerides) from baseline at week 12 between B. breve and placebo

4. The difference in change from baseline between B. breve and placebo in biomarkers of glycemic control (fasting blood glucose, HbA1c, fasting insulin levels) after 12 weeks of supplementation	
H04.1:
 
There is no difference in mean change in biomarkers of glycemic control (fasting blood glucose, HbA1c, fasting insulin levels) from baseline at week 12 between B. breve and placebo

5. The difference in change from baseline between B. breve and placebo in liver markers (AST, ALT, GGT, ALP) after 12 weeks of supplementation	
H05.1:
 
There is no difference in mean change in liver markers (AST, ALT, GGT, ALP) from baseline at week 12 between B. breve and placebo

6. The difference in change from baseline between B. breve and placebo in the frequency of bowel movements after 6 and 12 weeks of supplementation	
H06.1:
 
There is no difference in mean change in the frequency of bowel movements from baseline at week 6 between B. breve and placebo
 
H06.2:
 
There is no difference in mean change in the frequency of bowel movements from baseline at week 12 between B. breve and placebo

Summary statistics including number of participants, mean, median, standard deviation, minimum, and maximum will be obtained for each visit. Similar summary statistics will be obtained for each available change from baseline to each subsequent visit. Mean values will be displayed as graphs, with a separate line for each product, and error bars indicating  $\pm$  SEM. Mean changes from baseline will also be graphed similarly.

Continuous secondary outcomes #2 and # 6 will be assessed using linear mixed effects ANCOVA, the fixed effects will include the baseline measurements as covariate and group\*visit as the factor variables. The dependent variable will be the change at each visit.

Continuous secondary outcomes #1, #3, #4, and #5 will be assessed using ANCOVA, with the baseline measurements as covariate and group as the factor variable. The dependent variable will be the change from baseline at week 12.

Q-Q plots and residuals versus fitted values plots will be generated for the evaluation of the model adequacy. If the residual plots show violation of the model assumptions, log or other transformation of the dependent variable will be performed.

Between group differences will be assessed by two-sample t- test. If the outcome is not normally distributed, then Wilcoxon rank sum test will be used.

Within group differences will be assessed by paired t-test if the outcome is normally distributed and Wilcoxon signed rank test otherwise. P-values and 95% confidence intervals will be calculated.

For categorical variables, counts and percentages will be presented. The denominator for each percentage will be the number of subjects within the study group for that visit/week unless otherwise specified. Possible differences between groups will be assessed by using the two-tailed Chi-squared or Fisher's exact test, as appropriate.

The frequency of BMs will be calculated as the average number of BMs per day over the 7 days prior to baseline and 7 days prior to week 6 and week 12.

[The microbiota analysis outcomes (#7 and #8) will be covered in a separate SAP].

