## 9.5 Visit 3 (Week 6, 42 ± 3 days)

Participants will return to the clinic fasted for 12 hours, with the unused product, in addition to completed subject diaries, food records, daily bowel habits diaries and exercise diaries, for visit 3. Compliance calls will be made at fixed intervals.

Visit 3 assessments include:

1. Review concomitant therapies and adverse events
2. Collect unused investigational product; calculate compliance
3. Collect and review Subject Diary
4. Collect and review 3DFR
5. Collect and review Daily Bowel Habits Diary
6. Collect and review Exercise Diary
7. Seated resting blood pressure, heart rate, respiratory rate, and temperature measurements
8. Weight (BMI calculation), waist and hip circumference measurements (waist/hip circumference ratio)
9. Dispense investigational product and instruct participants on use
10. Dispense Subject Diary
11. Dispense 3DFR
12. Dispense Daily Bowel Habits Diary

Protocol 20BWHM:

A randomized, double-blind, placebo-controlled study to investigate the effects of a *Bifidobacterium breve* strain on fat loss in healthy adults

13. Dispense Exercise Diary
14. Dispense stool collection kits

The next visit will be scheduled for week 12 (EOS).

Reminders for participants prior to their next in-clinic visit:

1. Return to the clinic in a fasted state (12 hours or greater)
2. Maintain exercise intervention (20 min aerobic exercise x 3 days/week)
3. Abide by instructions for prescribed medications as per Section 7.3.1 and OTC medications, supplements, and food/drinks as per Section 7.3.2
4. Limit alcohol intake (<2 standard drinks per day or <10 per week)
5. Complete and return stool collections
6. Complete and return Daily Bowel Habits Diary
7. Complete and return 3DFR
8. Complete and return Exercise Diary
9. Complete and return Subject Diary
10. Return unused IP

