## **10.8 Dual-Energy X-Ray Absorptiometry (DXA) Scan**

The Dual-Energy X-Ray Absorptiometry Scan will be conducted at KGK clinic (London, ON) at visits 2 (week 0), and 4 (week 12) by trained technicians. Body tissue density will be measured by a form of X-ray radiation and converted into body fat and muscle mass percentage for assessment. Prior to the day of the DXA assessment, the coordinators will remind the participants to limit the amount of water and food consumption accordingly. A full body composition DXA scan will expose the participant to a total dose of <10uSV, depending on the size of the participant. This amount is less than a person is exposed to on an east to west coast flight within the USA and similar to the normal background radiation received over the course of a single day level (23, 24).

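### SAP 5.2 tests weight and BMI on week-12 change alone, leaving their week-6 values out of the model and departing without explanation from Protocol 12.3

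*SAP*

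**What the plan says.** Protocol 12.3: "Continuous secondary endpoints will be tested for between-group differences using repeated measures linear mixed-effects ANCOVA". The response there is change at each visit, with group by visit as fixed effects, baseline as covariate and a random effect for each participant.

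SAP 5.2 keeps a mixed model for outcomes 2 (circumferences) and 6 (bowel movement frequency) only. For the rest: "Continuous secondary outcomes #1, #3, #4, and #5 will be assessed using ANCOVA, with the baseline measurements as covariate", and the response is week-12 change. No reason is given for the narrowing.

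Outcome 1 groups weight and BMI with android/gynoid ratio and muscle mass, all labelled as DXA measures. DXA is done "at visits 2 (week 0), and 4 (week 12) by trained technicians". Weight is taken on scales at every visit (Protocol 10.1), and the week-6 visit lists "Weight (BMI calculation), waist and hip circumference measurements (waist/hip circumference ratio" as one step (Protocol 9.5).

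SAP section 7 fills all missing efficacy values by LOCF or multiple imputation. It does not choose between them or describe an imputation model.

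**The concern.** Week-12 ANCOVA is the natural model for the DXA items and for outcomes 3 to 5, which have one post-baseline measurement. Weight and BMI have two, and appear to have been carried along with the DXA items. Weight and waist, taken minutes apart at the same visits, therefore get different models, and one of these departs from the protocol.

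At stake is the treatment of a participant who has week-6 but no week-12 data. Such a person belongs to the ITT population, which asks only for some post-randomization efficacy information. A week-12 ANCOVA can include that person only after imputation. Under LOCF the week-6 change is relabelled as week-12 change. A likelihood-based mixed model would use the week-6 value as what it is, under missing at random, and still give the week-12 contrast.

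**Working it through.** **1. The plan's own sample size.** Protocol 12.1 states: "With a total sample size of 100 (50 per group; 40 completers), it is possible to detect a difference in mean change in percent body"; "body fat mass of 0.76% or 0.79 kg respectively, in a parallel design"; "two-sided unadjusted 5% significance level, 80% power and 20% attrition rate"; "standard deviations of 1.19% and 1.24 kg for percent body fat and body fat mass respectively".

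n per arm = 2(1.960 + 0.842)² (SD/difference)²
- Percent fat: 15.70 × (1.19/0.76)² = 38.5, so 39. The exact t-test gives 39.5, so 40.
- Fat mass: 15.70 × (1.24/0.79)² = 38.7, so 39. The exact t-test gives 39.7, so 40.
- Enrolled: 40/(1 − 0.20) = 50.

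The figure reproduces. It concerns DXA fat, so this point does not affect it. The documents give no SD for weight or BMI and no week-6/week-12 correlation, so everything below rests on assumed values.

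**2. Complete week-12 data.** A simulation used 300 runs, 40 per arm, correlation 0.7 and change SDs of 1.2 kg (week 6) and 1.8 kg (week 12). The week-12 estimates from ANCOVA and from a group-by-visit mixed model correlated 0.998, and each had an empirical SD of 0.414. The gain is essentially nil.

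**3. Missing week 12, compared with completers only.** With n6 per arm seen at week 6, n12 at week 12 and correlation ρ, the variance of the week-12 mean is proportional to ρ²/n6 + (1 − ρ²)/n12. Assume n6 = 45 and n12 = 40:
- ρ = 0.6: 0.36/45 + 0.64/40 = 0.02400, effective n 41.7
- ρ = 0.9: 0.81/45 + 0.19/40 = 0.02275, effective n 44.0

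That is 4% to 10% more than 40, or a standard error 2% to 5% smaller. The reference is a completers-only ANCOVA, which the SAP does not plan.

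**4. Missing week 12, compared with LOCF.** If the true effect is d6 at week 6 and d12 at week 12, and is the same in those who leave, LOCF estimates about (n12·d12 + (n6 − n12)·d6)/n6. Assume d6 = 0.40 and d12 = 0.80:
- 5 carried forward: (40 × 0.80 + 5 × 0.40)/45 = 0.756
- 10 carried forward: (40 × 0.80 + 10 × 0.40)/50 = 0.720
- If d6 = d12, there is no shrinkage.

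A simulation with correlation 0.7 and dropout related to week-6 change agrees. LOCF gave 0.71 to 0.77 for a true 0.80, while a likelihood-based model on observed data stayed at 0.80.

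**5. The price in precision.** Take ρ = 0.7 and week-12 SD = 1. The mixed-model variance per arm is 0.49/45 + 0.51/40 = 0.02364 with 5 missing, or 0.49/50 + 0.51/40 = 0.02255 with 10. The LOCF variance is (n12 + (n6 − n12)·r²)/n6², where r is the ratio of week-6 to week-12 SD.

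| Missing per arm | r | LOCF variance | SE ratio, mixed/LOCF |
|---|---|---|---|
| 5 | 1 | 0.02222 | 1.03 |
| 5 | 1.2/1.8 | 0.02085 | 1.06 |
| 10 | 1 | 0.02000 | 1.06 |
| 10 | 1.2/1.8 | 0.01778 | 1.13 |

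The simulation in step 4 found 2% to 4%, near the low end. LOCF looks more precise because it counts carried-forward values as observed week-12 data.

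**6. Covariance structure.** In the step 2 simulation, a random-intercept model reported an SE of 0.342 for an estimate whose true SD was 0.414. The nominal 1.96 limit then acts as 1.96 × 0.342/0.414 = 1.62, a two-sided error of about 10.5%. The covariance must therefore be unstructured.

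**The case against.** The strongest defence is that the SAP follows its endpoints. Outcome 1 is defined after 12 weeks only, while outcomes 2 and 6 are defined after 6 and 12 weeks. Giving one time point an ANCOVA and two a mixed model is coherent, and the protocol's blanket sentence could not apply to single-visit items anyway. This stands as a defence of the week-12 target. It does not explain why a measured week-6 value should not inform that target.

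Four stronger readings are tempting, and the documents do not support them:
- *The week-6 values are discarded.* They are not. SAP 5.2 summarises and graphs each visit, and the values can enter through LOCF or imputation.
- *A planned week-6 test is lost.* No week-6 hypothesis for weight or BMI exists in either document.
- *The SAP forgoes 4% to 10% of effective sample size.* That comparison is with completers only. A multiple imputation that used week 6 could recover similar information, and section 7 does not exclude one.
- *Changing the model removes LOCF.* It does not, because section 7 covers all missing efficacy values, including those of outcomes 2 and 6.

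The affected group may also be small. Protocol 7.5 asks for end-of-treatment evaluations at withdrawal where possible, and Protocol 11.2.2 asks participants who withdraw themselves to attend the remaining visits. Against that, 20% attrition is planned and withdrawals are not replaced.

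**Conclusion.** The point holds as a minor, inexpensive improvement to two secondary variables. SAP 5.2 leaves week-6 weight and BMI out of the inferential model and departs from Protocol 12.3 without saying why. The primary endpoint and sample size are untouched.

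The size depends on unknowns. With complete week-12 data there is no difference. With 5 to 10 participants per arm lost after week 6 and an effect still growing from 0.40 to 0.80, LOCF understates it by about 0.04 to 0.08 (6% to 10%). With an effect already complete by week 6 it does not. The argument is about estimating the stated week-12 quantity and settling the missing-data method in advance. It is not about power, because the lost shrinkage and the larger standard error roughly cancel (for example 0.80/1.03 = 0.78 against 0.76).

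**What to change.** In SAP 5.2:
- Separate weight and BMI from the DXA items of outcome 1, and drop the DXA label for them.
- Analyse observed changes at weeks 6 and 12 with a mixed model: baseline covariate, group by visit, and unstructured within-participant covariance rather than a random intercept alone.
- Report the week-12 group contrast as the result.
- Keep ANCOVA for android/gynoid ratio, muscle mass and outcomes 3 to 5, and note that this narrows Protocol 12.3 because those items have one post-baseline value.

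In SAP section 7, state that missing weight and BMI values are not replaced by LOCF before this model is fitted. Without that sentence the change in 5.2 has no effect.

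The cost is a few sentences, slightly more modelling work (a mixed model is already planned for outcome 2), and a standard error about 3% to 13% larger than LOCF would report under the assumptions above. If the sponsor prefers the week-12 ANCOVA, the SAP should say that the departure from the protocol is deliberate and why.
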